Study design. We will carry out a factorial experiment to test four candidate intervention components. Each component has two levels: "off" (the component is not received) or "on" (the component is received). The design is comprised of 16 experimental conditions (2⁴, Fig. 2), where each condition comprises a unique combination of intervention components. We wish to point out the design is not a 16-arm RCT. Factorial experiments separate component effects, enabling estimation of the main effect contribution of each component. Factorial experiments can be economical compared to alternative designs, because they require substantially fewer participants to achieve the same goals³⁵. For example, conducting four individual experiments using the RCT design, one for each component, would require N=2240 (560 participants per trial). Thus, the purpose and logical underpinnings of the factorial experiment are different from those of an RCT. The purpose of an RCT is a direct comparison of the efficacy of two or more versions of an intervention. By contrast, a factorial design never calls for a direct comparison of experimental conditions to see which one is best. Instead, the purpose is to identify which components show effectiveness. Efficiency comes from basing all estimated main effects on all 16 conditions in the factorial experiment. For example, the main effect of Component D will be estimated by comparing the mean outcome across Conditions 1-8 vs. across Conditions 9-16. All participants are included in the estimate of each main effect. Factorial experiments can have a small per-condition N and still achieve study aims if the total N is sufficient. All participants receive the core intervention. Condition 1 receives no other component. Conditions 2, 3, 5, and 9 receive one candidate component, Conditions 4, 6, 7, 10, 11, and 13 receive two candidate components, Conditions 8, 12, 14, and 15 receive three components, and Condition 16 receives all components.

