Specific structure of Component B: TMs are programmed into the Twilio program and sent automatically. The component is structured as follows: Participants first receive a brief orientation to the component (5 minutes) after the core session or baseline, and will put the study phone number into his/her/their phone. Then a test TM will be sent. TMs will be sent twice a week for 12 weeks, then 1 text/week for 8 weeks (total TMs = 32). Participants will be asked to provide a numerical response to the TM to indicate that it was read and received. These responses will be used to generate points (1 point/response), and participants will receive \$1 for each point (maximum \$32). This modest compensation will add interest to the component. "Gamification" principles will be used where participants will be sent a message at every 10 points such as "Achievement unlocked!" This is referred to as a "badge." Theoretical targets: circumvent cognitive biases.

Component C. Prize at 6-month FU if vaccinated for COVID-19 with documentary evidence (a gift bag with \$25 gift card and low-cost items costing no more than \$25, 3 reminder messages sent at regular intervals during intervention period). The goal of this component is to provide the participant with a type of "deadline" for vaccination and nudge them toward vaccination. This component will be explained to participants after the core session, ideally, or baseline (<5 minutes). We will put the study phone number into his/her/their phone. Then a test text message will be sent.

Timing will be: 1 month post-BL, 3 months post-BL, and 5 months post-BL.

The three reminder messages were refined by the CAB.

The reminder messages will read as follows:

1. "PRIZE REMINDER! Just a reminder that you are eligible to receive a prize at your 6-month followup interview if you get vaccinated for COVID-19 before that time! Just bring some documentation of the vaccination. Let us know if you have questions at PHONE or [contact]"

2. Don't miss out! A prize is waiting for you. Just bring some documentation of the COVID vaccination. Let us know if you have questions at PHONE or [contact]

3. Win a prize! Your 6-month follow-up can come with a reward – if get your COVID vaccine before then and bring proof to your visit. If you have any questions, reach out at PHONE or [contact]

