Aim 1: Identify which of four candidate intervention components contribute meaningfully to improvement in the primary outcome, receipt of the available COVID vaccine, with documentary evidence at the 6-month FU. The primary outcome for Aim 1 is receipt of the available COVID vaccine (documented) by the final follow-up. Logistic regression will estimate effects of components on the odds of receiving the available COVID vaccine. Intervention components will be effect-coded to estimate main effects and interactions of all four components (see **Equation 1**). The coefficient for an effect-coded main effect term (e.g., *b₁*), multiplied by two and exponentiated, will estimate the effect of the component (e.g., Component A) on the odds of vaccination. Similarly, the coefficient for an effect-coded interaction term, multiplied by two and exponentiated, will estimate interaction effects on the odds of vaccination. Similar logistic regression analyses will estimate effects on the secondary outcome.

Equation 1

$$\log\left(\frac{\pi_i}{1-\pi_i}\right) = b_0 + b_1 X_A + b_2 X_B + b_3 X_C + b_4 X_D + b_5 X_{A*B} + b_6 X_{A*C} + b_7 X_{A*D} + b_8 X_{B*C} + b_9 X_{B*D} + b_{10} X_{C*D} + b_{11} X_{A*B*C} + b_{12} X_{A*B*D} + b_{13} X_{A*C*D} + b_{14} X_{B*C*D} + b_{15} X_{A*B*C*D}$$

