Aim 3: Build the most cost-effective intervention package(s) from the components found to be efficacious in Aim 1. We will estimate the total cost of each experimental condition, rank them low to high, and remove any due to dominance (higher cost with lower effectiveness). Then, we will calculate the incremental cost-effectiveness ratio comparing each condition with the next lower cost condition, $[(cost_1 - cost_2)/(outcome_1 - outcome_2)]$, to yield for each component the *incremental cost per participant receiving vaccination* and *incremental cost per percentage point change in vaccination rate* (from Aim 1); we also will explore the *incremental cost per participant*.

The decision-making process will be led by [name] and include the study Co-Investigators ([name], [name], [name], [name], [name]) and consultants³⁵. The decisions will be reviewed with the CAB before being finalized. STEP 1: Carry out Aim 1 analyses, which detail the effectiveness of each component (% vaccinated) as well as interaction effects. This allows us to predict % vaccinated for each experimental condition, adjusting for any covariates. STEP 2: Carry out Aim 2 analyses, gualitative analyses, and the joint display to determine how components work and under what conditions, along with acceptability and feasibility. These data will be integrated into the implementation manual. STEP 3: Use cost estimates and incremental cost-effectiveness ratios from Aim 3 and rank-order experimental conditions by incremental cost-effectiveness ratio. STEP 4: Carry out same steps for influenza and consider that in decision-making. FINAL STEP: There may be several good options for improving outcomes at different levels of cost. We will create an efficient frontier for these experimental conditions using methods developed by our colleagues at NYU called decision analysis for intervention value efficiency (DAIVE), a decision-making framework for use in MOST²⁰¹. DAIVE is a user-friendly method for evaluating interventions based on a wide variety of decision-maker preferences, including those that involve multiple outcome variables. We have used DAIVE in a past study²⁰¹. Using data from the previous steps as inputs, DAIVE will be used to create an efficient frontier of interventions for COVID alone, influenza alone, and COVID and influenza together (where we can

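### Aim 3's next-lower-cost ICER rule does not assure the per-component ratios it promises, and strict dominance alone leaves out-of-order ratios in the ranking

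*Combined protocol and SAP*

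**What the plan says.** Aim 3 is to build the most cost-effective package(s) "from the components found to be efficacious in Aim 1". The Aim 3 paragraph costs each experimental condition, ranks conditions from low to high cost, and will "remove any due to dominance (higher cost with lower effectiveness"). It will then "calculate the incremental cost-effectiveness ratio comparing each condition with the next lower cost condition", using a printed formula that divides a cost difference by an outcome difference. The stated output is, *for each component*, an incremental cost per participant vaccinated and per percentage point of vaccination.

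The effectiveness figures come from STEP 1: "This allows us to predict % vaccinated for each experimental condition, adjusting for any covariates". STEP 1 does not say which model terms are kept. The only Aim 1 model written out is Equation 1, with components "effect-coded to estimate main effects and interactions of all four components": an intercept and 15 terms for 16 conditions. STEP 3 rank-orders conditions by their ratio. In the final step, "Using data from the previous steps as inputs, DAIVE will be used to create an efficient frontier of interventions".

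**The concern.** Ratios between cost neighbours describe moves between packages. Neighbours often differ by a swap, or by several components, and such a step gives no ratio for any one component. An efficacious component can therefore leave Aim 3 without the figure the plan promises.

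Precision suffers too if condition rates are the outcome. The Study design section says "Efficiency comes from basing all estimated main effects on all 16 conditions in the factorial experiment", but a ratio between two neighbouring conditions then uses only two of the 16.

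Two further points bear on package choice. Strict dominance does not remove a condition that is beaten by a mix of a cheaper and a dearer one (extended dominance), so its ratio stays in the STEP 3 ranking and distorts the one above it. And if condition predictions come from a saturated model, deletion on point estimates is partly a matter of chance. The optimized package is the trial's main product.

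**Working it through.** **Inputs from the documents (Power Analysis).** 28 × 16 = 448 complete cases; 448 / 0.80 = 560 enrolled; 560 / 16 = 35 per condition. These reproduce. Overall uptake is 40% and the target odds ratio (OR) is 1.9.

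**Assumed, because the documents give none.** Component costs and the efficacy screen. All simulated percentages depend on these.

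**1. The component ratio.** Let A be cheaper and B dearer and more effective. Cost and effect both rise along none, A, B, A+B, so nothing is dominated. The neighbouring steps are +A, A→B, and B→A+B (which is +A again). None of them is +B.

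Example with ORs 1.7 (A) and 2.1 (B), overall 40%: uptake is 25.7%, 37.0%, 42.1% and 55.2%. The middle step spans 42.1 − 37.0 = 5.1 points and is a swap. B's factorial risk difference is [(42.1 − 25.7) + (55.2 − 37.0)] / 2 = 17.3 points, and no step in the sequence estimates it.

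More generally, with additive distinct costs and every subset present, only the cheapest component can form a one-component step. If a dearer component k is added to S, then either S plus the cheapest component or S plus k minus the cheapest lies between them in cost. Dominance removal can create further steps, but does not assure them.

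Noise-free draws (ORs 1.5–2.5, costs 10–150, 4,000 per case) in which every efficacious component got a one-component step:

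| Efficacious components | 2 | 3 | 4 |
|---|---|---|---|
| Additive costs | 50% | 17% | 5% |
| Component C's cost rising with uptake | 50% | 16% | 4% |

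The second row is there because Component C is a "Prize at 6-month FU if vaccinated for COVID-19", so its cost depends on uptake.

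**2. Precision at 40% uptake, 28 per condition.**
- One condition: √(0.24/28) = 9.3 points.
- Difference of two conditions: √(0.48/28) = 13.1 points.
- Factorial main effect: 2√(0.24/448) = 4.6 points.
- With 35 per condition the last two become 11.7 and 4.1.

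**3. Extended dominance.** Put illustrative costs of 40 (A) and 80 (B) on the same example, with unrounded rates:
- A against none: 40 / 0.1133 = 353.
- B against A: 40 / 0.0505 ≈ 793.
- A+B against B: 40 / 0.1318 ≈ 304.

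The ratios are out of order. B is extendedly dominated, yet the rule keeps it, and A+B then appears to have the best ratio. With B removed, A+B against A is 80 / 0.1822 = 439, which is less favourable than A's 353. Under the assumptions of item 1, out-of-order ratios occurred in 51%, 86% and 97% of noise-free draws with two, three and four efficacious components.

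**4. Dominance if predictions are saturated.** Equation 1 has 16 parameters for 16 conditions, so its predictions equal the observed condition rates apart from covariates. Simulation: OR 1.9, 28 per condition, costs 25/40/80/150 in all 24 orders, screen at Wald z > 1.96, candidates limited to packages of components that pass. Percentage of screened trials in which the package of exactly the active components was deleted:

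| Active components | 1 | 2 | 3 | 4 |
|---|---|---|---|---|
| Saturated predictions | 9% | 14% | 18% | 20% |

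Repeat runs with separate code moved these by up to about 3 points. With 35 per condition the range is about 7% to 20%. A reduced model (main effects plus two-way terms kept at p < .05) gives 1–3%, and main effects alone under 1%.

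**The case against.** Costing mutually exclusive packages, removing dominated ones and differencing against the next cheaper is the ordinary sequential method, and the 16 conditions are such packages. STEP 3 and the final frontier work on conditions and never use a component ratio. In the example B does get a ratio, against A, which is a relevant contrast when choosing packages. This stands. A reader might infer that the rule selects the wrong package because component ratios are missing; the documents do not support that. What fails is a promised output.

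The ingredients of a component ratio are also planned already: Aim 1 component effects, and the resource tracking under Tracking program time and costs. The words *from Aim 1* could be read as pointing to those effects. But the printed formula still differences neighbouring conditions, so the text needs a decision either way.

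A reader might also infer that the plan will delete the right package. Two things count against this. Aim 3 seeks one or more packages and leaves the choice to end users, so it does not define the package of all active components as the right one. And saturated prediction is one reading of STEP 1. When deletion did occur, the true uptake lost was about 15 points, but averaged over screened trials it was 1.4 to 3.2 points, with a cheaper substitute.

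Finally, the decision analysis (DAIVE) may treat uncertainty or restore deleted conditions, and its efficient frontier may remove extendedly dominated ones. The documents do not say, so it cannot be claimed that no uncertainty reaches the decision.

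**Conclusion.** The concern holds in three parts of different strength.

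- **Not conditional on any cost figure or model:** the next-lower-cost rule does not assure a ratio for each component. It fails whenever the dearer of two efficacious components is also the more effective. The percentages in item 1 illustrate this; the logical gap does not depend on them.
- **Decision-level:** only strict dominance precedes the STEP 3 ranking, so extendedly dominated conditions stay in it. Under the assumed costs and effects this happens in about half of cases with two efficacious components and in most cases with three or four.
- **Conditional:** if STEP 1 keeps every Equation 1 term, chance deletion of the package of exactly the active components runs at roughly 9% to 20% of screened trials. Under a reduced model the risk is small.

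Aim 1 and the sample size are unaffected. The plan should be corrected before the Aim 3 analysis, because its outputs feed the trial's main product.

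**What to change.** 1. Compute each component's ratio from the factorial model: its incremental cost (with Component C's prize costed at predicted uptake) divided by its model-based risk difference, using all participants. Report the range across settings of the other components. If component ratios are not wanted, delete the words *for each component*.
2. Use sequential ratios only to compare packages, after both strict and extended dominance. This does not replace item 1. In a check with extended dominance and main-effects predictions, every retained component had its own step in only 58–79% of trials with four active.
3. State the prediction model for STEP 1: main effects plus interactions kept by a pre-stated rule, in place of the saturated model.
4. Carry bootstrap or posterior uncertainty into dominance, the ratios and the DAIVE inputs, instead of deleting conditions on point estimates. Say whether removed conditions can re-enter.

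The cost is wording and some programming, with no new data. There are two downsides. A weak true interaction may be dropped. And a pooled ratio is an average: with four components at OR 1.9 the mean gain is 14.3 points, but the first component added gains 25.2 − 15.1 = 10.1. The pooled ratio therefore understates that step's cost per vaccination by 1 − 10.1/14.3 ≈ 29%, which is why the range belongs beside it.
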